### **Initial Assessment**

After obtaining informed consent, an initial assessment will be conducted with participants. Participants will be asked to provide a baseline CO breath test and a urine sample to ascertain smoking status. If a candidate is deemed ineligible or chooses not to participate, they will be provided with information from the American Lung Association and referred to the Maryland Quit Line. Eligible participants will complete the baseline questionnaire which will include sociodemographic information, aspects of smoking history (e.g., years, quit attempts, etc), smoking urges, withdrawal symptoms and reinforcing effects of smoking, confidence to quit smoking, reasons to continue to smoke (pros) and barriers to quitting (cons), and perceived vulnerability to smoking-related illnesses, as well as other domains. A certified smoking cessation interventionist (SCI) will deliver standardized smoking cessation counseling using the National Cancer Institute's 5A's model (described below in section e). After brief counseling, all participants will set a quit date within the next 2 weeks and receive their randomized group assignment.

Participants in the COach2Quit arm will be provided with an individualized carbon monoxide (iCO) monitor along with instructions on the use of the monitor and the COach2Quit application. The SCI will help the participant install the COach2Quit app on their phone, guide them through completing an initial CO breath test using their iCO monitor connected to their smartphone, and answer any questions they may have. Participants will be requested to use their iCO monitor at least twice per day and answer a few questions about the amount smoked that day. The participant will be informed that their results will be sent to the study team through the application each time the participant uses their iCO monitor.

### **b. Study duration and number of study visits required of research participants.**

Dated: 15 May 2017

Each participant will have a total of 3 study visits: baseline assessment, 2-week follow-up, and 1-month follow-up. The participant will also receive weekly follow-up phone calls. Thus, the participant will remain in the study for a total duration of approximately 1.5 months, depending on quit date. The complete schedule of study visits (for both groups) is detailed in Table 1. We anticipate a period of 4 months to complete this pilot trial.

**Table 1:** Visit schedule for pilot randomized controlled trial

Pilot RCT			
Visit #	Timeline	Schedule	Content
1	Day 0	Baseline, Counseling	CO breath test, urine sample; baseline assessment; study group assignment
2	2-weeks	Follow-up	CO breath test, urine sample, cognitive and behavioral processes questions
3	1-month	Follow-up	CO breath test, urine sample; cognitive and behavioral processes questions

**c. Blinding, including justification for blinding or not blinding the trial, if applicable.**

This will be an open-label trial in which neither the subjects nor the study coordinator will be blinded as to treatment assignment after randomization. However, the study interviewer conducting baseline breath CO and urine testing will be blinded as to treatment arm of the individual participants to decrease bias.

**d. Justification of why participants will not receive routine care or will have current therapy stopped.**

Participants will be excluded from the study if they are currently on NRT or other smoking cessation therapy. The care of patients at any Johns Hopkins facilities will not be affected in any way, regardless of whether they decline to participate in the study, remain in the study or drop out of the study.

**e. Justification for inclusion of a placebo or non-treatment group.**

Eligible participants will be randomized to receive one of two cessation strategies: (1) COach2Quit or (2) brief anti-smoking advice. All participants will receive advice to quit smoking and self-help materials in a standardized fashion. The advice to quit smoking message (3 min.) will follow the 5A's model for smoking cessation counseling. This is a simple smoking cessation counseling strategy with 5 discrete components: (1) Ask about smoking at every opportunity; (2) Advise the patient to quit smoking; (3) Assess readiness to quit; (4) Assist the patient in quitting; and (5) Arrange follow-up. The 5A's model is endorsed by the World Health Organization in international settings as well as the US.

**f. Definition of treatment failure or participant removal criteria.**

Participants will be discontinued from the study if they (1) ask to be removed from the study (2) are found to be using other smoking cessation treatments (3) develop a medical condition precluding the use of the iCO monitor such as COPD (4) develop a serious adverse event (SAE).

**g. Description of what happens to participants receiving therapy when study ends or if a participant's participation in the study ends prematurely.**

The participant will continue to receive care at these facilities should he/she choose to leave the study for any reason. If a participant leaves the study prematurely due to an adverse event, text messages will stop being sent to them.

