**5. Inclusion/Exclusion Criteria**

Coach2Quit RCT protocol  
Version: 2.4

Dated: 15 May 2017

Participants are eligible to take part in this trial if they meet the following **inclusion criteria**: (1)  $\geq 18$  years of age; (2) current, daily smokers, (3) agree to participate and anticipate to be living in Baltimore for at least 2 months, (4) own a phone that is compatible with the app, (5) be willing to set at baseline assessment a quit date within 2 weeks.

Participants will be **excluded** if they (1) are suffering from any unstable medical condition *precluding the use of the CO monitor* (e.g. severe COPD); (2) are currently using smokeless tobacco including e-cigarettes; (3) are currently using NRT or other smoking cessation treatment, (4) are pregnant, determined by participant self-report or (5) have a negative baseline result on both urine cotinine AND CO monitor.

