### **c. Statistical plan including sample size justification and interim data analysis.**

#### **Data analysis plan**

**Overview** The primary outcome measure for the RCT is proportion of participants with biochemically verified smoking cessation as of 1-month; the primary exposure is study arm, brief-advice only vs. COach2Quit. We will compare proportions of smoking abstinence between study arms at 1-month.

Covariates of interest (e.g. sex, age, race, ethnicity, education, income, smoking history) will be assessed for relationship to prevalence of quitting. These comparisons will utilize the chi-square test for categorical variables and either the Student's t-test or the Wilcoxon signed rank test for continuous variables. Multivariate logistic models will be generated using forwards stepwise model selection, including study arm and all variables with  $p < 0.2$  or odds ratio  $< 0.5$  or  $> 2.0$  at the univariate level, ultimately generating the most parsimonious model.

We will conduct intent-to-treat analyses, providing the purest analysis for an RCT. For these analyses, participants who are lost to follow-up will be considered smokers from the date of last contact. This approach is conservative, as it will likely include participants who have not received either study intervention, but point estimates will be biased towards the null. This approach has been widely adopted in smoking cessation studies. We will compare rates of losses to follow up across the study arms, and look for differences in characteristics of those lost between the arms.

We will analyze number of smoke-free days obtained from questionnaires by comparing the proportions of smoke-free days between arms with a Wilcoxon signed rank test. We will estimate either the absolute difference in proportions, or after a  $\log(\text{days smoke-free}+1/\text{total days of follow up})$  transform if appropriate, with 95% confidence intervals. We will also measure durability of treatment effects using consecutive visits with biochemically verified smoking cessation.

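### The removal rule can end outcome collection because of other cessation aids, leaves it unclear whether e-cigarettes count, and is not matched by a scoring rule for those affected

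*Combined protocol and SAP*

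**What the plan says.** **Entry.** Section 5 keeps two classes apart. Exclusion 2 covers people who "are currently using smokeless tobacco including e-cigarettes". Exclusion 3 covers people who "are currently using NRT or other smoking cessation treatment".

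**Follow-up.** Among the grounds for removal in section 4f is that participants "are found to be using other smoking cessation treatments". E-cigarettes and smokeless tobacco are not named. The section does not say who applies the rule. Its heading mentions treatment failure, but its text does not say that a removed participant is scored as one.

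**Blinding.** Section 4c says that "neither the subjects nor the study coordinator will be blinded as to treatment assignment after randomization". It adds that "the study interviewer conducting baseline breath CO and urine testing will be blinded", and so states assessor blinding for the baseline tests only.

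**Outcome.** The primary measure in section 7c (Data analysis plan) is the "proportion of participants with biochemically verified smoking cessation as of 1-month". Section 4a names two verifying biomarkers, breath CO and urine cotinine, at baseline, 2 weeks and 1 month. Section 6 takes a CO reading of 10 ppm or below as abstinence, and says that cotinine is detectable after NRT as well as after smoking. Section 7c commits to intent-to-treat and counts those lost to follow-up as smokers from last contact.

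**Detection.** For the 2-week visit, Table 1 lists "CO breath test, urine sample, cognitive and behavioral processes questions"; the 1-month row has the same elements. Weekly calls go to both arms, but their content is not described.

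**The concern.** Every participant sets a quit date, so some replacement of cigarettes by another product is foreseeable. Read literally against the two classes in section 5, the removal rule does not reach a participant who starts vaping. Read broadly, with vaping as a cessation aid, it does. The text supports either reading, and the choice may fall to staff who know the arm.

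The second problem does not depend on e-cigarettes. Even for products that the rule plainly covers, removal is triggered by behaviour after randomisation and can stop the 1-month tests. An intent-to-treat comparison needs those outcomes. Section 7c has a rule for losses to follow-up, but a participant removed by the study is not obviously lost to it.

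At stake is the estimate itself. The Sample Size paragraph says that the pilot exists to supply estimates for later studies. If product use is neither asked about uniformly nor recorded, its effect on that estimate cannot reliably be reconstructed afterwards.

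**Working it through.** The plan gives no figure on this point, so there is none to reproduce. The check has two parts.

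**1. Following one participant through the text.** Take someone who stops cigarettes, vapes nicotine, and at 1 month would have CO of 10 ppm or below and a positive cotinine. That vaping gives this pattern is an inference: section 6 describes non-cigarette nicotine in urine for NRT only.

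| Reading of section 4f | Further rule needed, not stated in the plan | Primary outcome |
|---|---|---|
| Covered, removed | Removed treated like lost to follow-up | Smoker |
| Covered, removed | Removed left out of the analysis | Not counted |
| Covered, removed | 1-month tests still obtained | As for a retained participant |
| Not covered, retained | CO alone verifies | Abstinent |
| Not covered, retained | Either test negative is enough | Abstinent |
| Not covered, retained | Both tests must be negative | Smoker |

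The result depends on three unstated items: the scope of the removal rule, the scoring of removed participants, and the way CO and cotinine combine. If both tests must be negative and removed participants count as smokers, the two readings of section 4f give the same answer.

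**2. Sensitivity of the estimate.** Inputs from section 7c (Sample Size): 150 participants, 1:1, anticipated rates 20% and 10%.

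- Per arm: 150 / 2 = 75.
- Expected quitters: 75 × 0.20 = 15 and 75 × 0.10 = 7.5.
- Expected difference: 15/75 − 7.5/75 = 10.0 points.
- Standard error: √(0.20 × 0.80/75 + 0.10 × 0.90/75) = 0.0577. The Wald 95% interval is 10.0 ± 1.96 × 5.77, or −1.3 to 21.3 points.
- One person rescored in one arm: 1/75 = 1.33 points.

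The documents give no number of people affected, so *k* below is an assumption. The app-arm column is (15 − k)/75 − 7.5/75, the advice-arm column 15/75 − (7.5 − k)/75.

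| k quitters rescored as smokers | App arm only | Advice arm only | Same k in both arms |
|---|---|---|---|
| 1 | 8.7 | 11.3 | 10.0 |
| 3 | 6.0 | 14.0 | 10.0 |
| 5 | 3.3 | 16.7 | 10.0 |

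Equal handling protects the difference but not the arm-specific rates: with k = 3 in both arms they become 12/75 = 16% and 4.5/75 = 6%.

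**The case against.** The strongest reply is that cotinine already deals with this. Two biomarkers are named, every participant gives urine at each visit, and a CO-negative, cotinine-positive result would flag other nicotine use in both arms alike. If both tests must be negative, a nicotine vaper would be expected to be scored a smoker. This stands as a condition. It does not close the point, because section 7c never says that both must be negative, and it does not help a participant whose tests were stopped by removal.

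It can also be said that this is a pilot with no claim to power. That limits the consequences for inference. It does not excuse distortion of the estimate, which is the pilot's product.

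Four stronger readings are tempting, and the documents do not support them:

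- *That the unblinded coordinator decides who is removed.* Section 4c says that the coordinator is unblinded, but no section assigns the decision. It may fall to unblinded staff; no more can be said.
- *That a removed participant is scored a smoker.* The smoker rule mentions losses to follow-up only.
- *That detection is better in the app arm.* That arm has more contact, but the app questions described concern the amount smoked and the CO result. The calls go to both arms, Table 1 is a summary, the questionnaires are not in the documents, and the breath-test section adds questions on smoking since the last visit. Unequal detection is plausible, not shown.
- *That a given share of outcomes turns on this decision.* No uptake figure is given. Someone who tries an e-cigarette and keeps smoking is a smoker under any rule; only CO-negative substitutes are affected.

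**Conclusion.** The point holds in a limited form. Sections 4f and 5 do not match, and the text cannot settle whether starting to vape leads to removal. Removal on post-randomisation product use can cut off the primary outcome in an open-label trial that promises intent-to-treat analysis, and the plan does not say how those removed are scored. A retained vaper can be counted a quitter only under a rule in which a negative cotinine is not required.

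Neither the size nor the direction of any bias is established. The figures show sensitivity only: 1.33 points for each person rescored in one arm, with 75 per arm and the plan's anticipated rates, and no change in the difference when both arms are handled alike. The conclusion assumes that removal from the study ends the visits, which is the natural reading of section 4f but is not spelled out, and that vaped nicotine raises cotinine but not CO.

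**What to change.** 1. Reconcile section 4f with section 5, so that it is clear which products the removal rule covers and who applies it. Which removal rule is clinically right is for the investigators; no view is taken here.
2. State that, whatever happens to a person's participation, the 1-month outcome is still sought from every randomised participant who has not withdrawn consent.
3. In section 7c, state how removed participants are scored and how a CO-negative, cotinine-positive result is scored.
4. Ask one identically worded question on NRT, cessation medication, e-cigarettes and smokeless tobacco in both arms, at the existing weekly calls and the 2-week and 1-month visits.
5. Report use by arm, with one pre-stated sensitivity analysis that counts users as not abstinent.

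The cost is protocol wording and one question within contacts already planned. The downside is that some participants in the main analysis will have used other products; the sensitivity analysis shows how much that matters.

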## **4. Study Procedures**

### **a. Study design**

**Overview:** The goal of this randomized controlled trial is to assess the efficacy of the novel COach2Quit smartphone application by determining whether the use of this app reduces smoking more than brief anti-smoking advice alone. This will be a two-arm individually randomized trial and participants who are currently smoking will be assigned 1:1 to either study arm. Smoking behavior will be measured through self-report at baseline, 2-week and 1-month follow up visits. Smoking behavior will also be verified by 2 biomarker measurements: carbon monoxide breath test and urine cotinine, collected at baseline, 2-week and 1-month follow-up visits. In addition, participants will receive weekly follow-up calls. **The primary outcome will be smoking cessation at the 1-month follow-up visit.**

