### **Carbon Monoxide Breath Test**

When a smoker smokes a cigarette, or any tobacco product, he/she breathes in carbon monoxide, which competes with oxygen to combine with hemoglobin. Hemoglobin has a 200-250 times greater affinity for CO than for oxygen, thus greatly interfering with the necessary binding of oxygen to hemoglobin. Several machines are available to measure the COHb level in the blood of smokers, providing a means of measuring recent exposure to cigarette smoking. For our study, a point of care test for measuring carbon monoxide will be conducted via the piCO Smokerlyzer from OPS Medical, designed specifically for smoking cessation programs and tobacco control programs. Carbon monoxide will be measured in an exhaled breath in parts-per-million (ppm). **A reading of  $\leq 10$  ppm will indicate abstinence.** Participants will be asked about their smoking history since their last visit and on the day of the CO test. If the participant has a positive CO test, they will be further counseled for smoking cessation if enrolled in the clinical trial. If not in the clinical trial, they will be provided with information from the American Lung Association and referred to the Maryland Quit Line. Results will be recorded and labeled with the participant's study ID, and the participant will see their results immediately and the results will be explained to them.

Dated: 15 May 2017

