##### **b. Steps taken to minimize the risks.**

Risks to confidentiality will be minimized by the following procedures: participant interviews will be conducted in a private area of the clinic, study records will be stored in locked cabinets in secure locations, study records will be accessible only to authorized study staff, databases will be password-protected and accessible only to authorized study staff. Study records and databases will not be accessible by employers, and study participation will not affect employment status. All study personnel will complete a course in research subjects' protection. Protected Health Information (PHI) that will be collected from participants are name, age, and phone number. All PHI will be stored on paper, not electronically, in a locked cabinet in a secure location, and PHI will only be accessible to authorized study staff. **No PHI will be collected or stored online or within the smartphone application.** All participants will receive a unique user ID that will be used in the smartphone application. This ID will be linked to their PHI that will be recorded on paper and stored securely. The PHI will be owned by the Principal Investigator, [name], at JHU.

A detailed protocol will be established for all research staff to be trained to identify an Adverse Event (AE) or Serious Adverse Event (SAE) and to follow in the event of an AE or SAE. The research staff person identifying an AE or SAE will immediately report the event to [name]. The study staff will discuss the situation with [name], and submit the appropriate paperwork to the IRB within 24 hours of becoming aware of the event. These events will also be documented during the IRB's yearly continuation review of the project.

Dated: 15 May 2017

This study will use the NIDA's Common Adverse Events (AEs) and Serious Adverse Events (SAEs) definitions for clinical research. Adverse events are defined as any event or outcome that has resulted in harm to the participant, has affected the participant detrimentally, has worsened as a result of participation in the study, or that has resulted in increased risk to the participant or others whether or not the risk actually results in harm. Specific SAEs include:

- death;
- serious injury;
- a life-threatening experience;
- hospitalization;
- a persistent or significant disability or capacity;
- suicidal ideation/attempts;

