In addition, all reactions to the study device that are not considered an SAE will be documented as an AE. The PI will be available by phone for any study issues.

Any AE that occurs between the time a participant signs the informed consent form and the time he or she departs the study at the end of the final follow-up visit will be captured and recorded. In the event that the participant is withdrawn from the study due to an AE, it will be recorded on the case report forms as such. The participant will be followed and treated by the Investigator until the abnormal parameter or symptom has resolved or stabilized. It is up to the clinician to determine that the SAE is either resolved, or that it has reached a stable state, after which no further follow-up is necessary. There will be documentation to support that determination.

Once an AE or SAE is known, research team members at the study site should ensure that participants receive appropriate care. All actions taken by the study staff after observing an AE or SAE should be documented, including increased monitoring of the participant, suspension of the treatment, etc.

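### Section 4f takes participants out of the study, with no later smoking-outcome visit, for an SAE, a condition ruling out the iCO monitor, or other cessation treatment, although the 1-month outcome could still be at least partly collected

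*Combined protocol and SAP*

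**What the plan says.** Section 4f places four criteria under one opening: "Participants will be discontinued from the study if they". They are (1) the participant's own request, (2) use of another cessation treatment, (3) the participant may "develop a medical condition precluding the use of the iCO monitor such as COPD", and (4) a serious adverse event. The section does not separate stopping the intervention from ending outcome follow-up.

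Section 4g adds that usual care continues, and: "If a participant leaves the study prematurely due to an adverse event, text messages will stop being sent to them".

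Section 8b includes "hospitalization" in its list of serious adverse events and attaches no condition that the event be related to the study. For someone withdrawn after an adverse event it says: "The participant will be followed and treated by the Investigator until the abnormal parameter or symptom has resolved or stabilized". It also names suspending treatment as one possible action after an event.

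On devices and measurement:
- Section 4a, Initial Assessment: "Participants in the COach2Quit arm will be provided with an individualized carbon monoxide (iCO) monitor".
- Section 4a, Study design, uses self-report and adds: "Smoking behavior will also be verified by 2 biomarker measurements: carbon monoxide breath test and urine cotinine".
- Section 6, Carbon Monoxide Breath Test: "a point of care test for measuring carbon monoxide will be conducted via the piCO Smokerlyzer from OPS Medical".

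Section 7c promises an intent-to-treat analysis, treats those lost to follow-up as smokers from their last contact, and compares losses between arms. It does not mention participants removed under 4f.

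**The concern.** Stopping an intervention and leaving a trial are different events, and an intent-to-treat comparison needs outcomes after the first as well. Under 4f, a participant who is willing to attend at 1 month can be taken out because of something that happened after randomisation. If that person had quit, the analysis either records a smoker or loses the participant. Comparing losses by arm would describe an imbalance but would not recover the outcomes.

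Criterion (3) is the clearest mismatch, since it ties removal to a device that only the app arm receives and that the outcome does not use. Criteria (2) and (4) may well be met more often. Section 4a recruits recently discharged inpatients, so an unrelated readmission would trigger (4). The trial is open-label, so use of other treatments could differ by arm. The pilot is meant to supply estimates for a larger trial, and a rule that discards outcomes could be carried forward into it.

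**Working it through.** The point is mainly textual, and the plan has no figure to reproduce: section 7c, Sample Size, gives 150 participants, 1:1 allocation and rates of 20% and 10%, with no power or alpha.

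**Step 1. Does any text keep removed participants to 1 month?** Section 4f ends study participation. Section 4g deals with care and messages. Section 8b continues clinical follow-up until the event settles and names no smoking assessment. The visit table in 4b makes no provision for removed participants. So no outcome visit is specified after removal.

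**Step 2. Could the outcome still be collected?** The personal iCO is the app-arm intervention. The 1-month outcome uses self-report, urine cotinine and the clinic piCO. Self-report and cotinine need no breath device. The piCO does need exhaled breath, so a condition under (3) may rule it out too. Collection is then partial, not nil.

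**Step 3. Size per removal, if counted as a smoker.** Inputs: 150/2 = 75 per arm; rates 0.20 and 0.10. Assumption: those removed would have quit at their arm's rate.
- Standard error of the difference: sqrt(0.20 × 0.80/75 + 0.10 × 0.90/75) = 5.77 points.
- One app-arm removal: 0.20/75 = 0.27 points off the difference.
- One control-arm removal: 0.10/75 = 0.13 points on to it.

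**Step 4. Criterion (3) alone.** The documents give no rate. I assume 0 to 2 removals per arm; 0 is plausible.

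| Removed (app, control) | Expected difference, points | Shift | Shift / SE |
|---|---|---|---|
| 0, 0 | 10.00 | 0 | 0 |
| 2, 0 | 9.47 | -0.53 | 0.09 |
| 2, 2 | 9.73 | -0.27 | 0.05 |
| 0, 2 | 10.27 | +0.27 | 0.05 |

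If both of two removed app-arm participants had quit, the loss is 2/75 = 2.7 points, with probability 0.20² = 0.04.

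**Step 5. Criteria (2) to (4) together.** With an assumed share d removed and counted as smokers, the difference is 0.20(1 - d) - 0.10 for the app arm only, 0.10(1 - d) for both arms equally, and 0.20 - 0.10(1 - d) for the control arm only.

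| d | App only | Both arms | Control only |
|---|---|---|---|
| 2% | 9.6 | 9.8 | 10.2 |
| 5% | 9.0 | 9.5 | 10.5 |
| 10% | 8.0 | 9.0 | 11.0 |
| 15% | 7.0 | 8.5 | 11.5 |

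These shares are illustrations, not forecasts. The last row means about 0.15 × 75 = 11 removals in an arm.

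**Step 6. If removed participants are left out instead.** With two app-arm participants left out, and removal unrelated to quitting, the expected rates do not change and the standard error becomes sqrt(0.16/73 + 0.09/75) = 5.82 points.

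**The case against.** The strongest reply is that little is at stake and much is already handled. Section 5 excludes people with an unstable condition that rules out CO monitoring, and participation lasts about 1.5 months, so criterion (3) should rarely be met. Section 7c commits to intent-to-treat, and its rule for losses, read naturally, keeps removed participants in the denominator. The pilot is declared not powered. All of this stands and limits the size of the point. It does not justify creating losses among people willing to attend, and 7c leaves it unsaid whether removal by rule counts as loss to follow-up.

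Removal under criterion (2) is defensible: other treatment is a baseline exclusion, and section 6 says nicotine replacement also yields detectable cotinine. That is a reason for a separate verification rule, and it adds to the cost of the change.

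Three stronger readings are tempting, and the documents do not support them:
- A reader might infer that all follow-up stops after a serious adverse event. Section 8b continues safety follow-up and contemplates suspending treatment. Only the smoking outcome is left without a visit.
- A reader might infer that, because the iCO is not the outcome device, the full outcome is recoverable. A condition that prevents use of one breath device may prevent use of the other.
- A reader might infer a bias against the app arm. Section 4f applies to participants in both arms; that (3) would act mainly in the app arm is an inference.

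**Conclusion.** The point holds as a minor design weakness. As written, 4f gives up 1-month outcomes that could be at least partly collected, for three reasons other than withdrawn consent, and this conflicts with the intent-to-treat aim in 7c.

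The effect is probably very small. For criterion (3) it is at most 0.09 of a standard error under the assumed 0 to 2 removals per arm. For the three criteria together it cannot be sized from the documents, which give no removal rates. Direction depends on the arm, so the statement in 7c that counting losses as smokers pulls estimates towards the null need not hold for control-arm removals. The figures rest on the planned rates, on removed participants quitting at their arm's rate and, except in step 6, on their being counted as smokers. Nothing here shows that the primary comparison would be materially distorted.

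**What to change.** Reword 4f so that only the participant's own withdrawal of consent ends outcome follow-up.

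- **Criteria (3) and (4):** stop the iCO or app intervention only. Keep the 2-week and 1-month visits, with self-report, urine cotinine and clinic breath CO where feasible.
- **Criterion (2):** keep the same visits and record the other treatment. State that participants on nicotine replacement are verified by breath CO, because their cotinine can be positive without smoking.
- **Analysis (7c):** analyse everyone in the assigned arm, and say that removed participants with no 1-month result are counted as smokers.

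The cost is one or two sentences in 4f for criteria (3) and (4), a sentence in 7c, and a verification rule for criterion (2), which affects how the primary outcome is defined. No visits are added beyond those already scheduled. The downsides are slight dilution from app-arm participants who no longer use the monitor, and verification by cotinine alone where a breath test is not feasible. A participant on nicotine replacement who cannot give a breath sample would have no usable biomarker, so the rule should also say how that case is counted.
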